4.3.2 Imputation of mRS Score

Deceased subjects will be assigned scores of 6 on the mRS.

Single Imputation (SI): To follow the composite strategy, the following approach will be used to impute missing mRS data at Day 90:

- if the participant is known to be dead at Day 90, they will be considered to be a non-responder and the mRS will be imputed as 6
- if the mRS was obtained at the Day 30 assessment or later and the participant is documented to be alive or the mortality status is unknown at Day 90, the Day 30 (or later) assessment will be carried forward as the Day 90 mRS value
- if both the Day 30 and Day 90 mRS scores are missing but the participant is documented to be alive at Day 90 they will be considered to be a non-responder and the mRS will be imputed as a 5
- if both the Day 30 and Day 90 mRS scores are missing and the mortality status of the participant is unknown at Day 90 they will be considered to be a non-responder and the mRS will be imputed as a 6.

If more than 5% subjects randomized are missing the mRS score at Day 90, additional imputation methods will be employed as follows:

Multiple Imputation (MI): The multiple imputation method assumes a Missing-At-Random (MAR) mechanism, which is a reasonable assumption for missingness not due to death. For the MI model, 50 imputations will be generated using PROC MI of SAS[®]. Imputation will be performed using the Fully Conditional Specification (FCS) logistic regression model. For each of the 50 datasets, missing mRS responders status (yes or no) will be imputed using a logistic regression model including treatment group, the mRS responder status at prior post-randomization visits, baseline mRS score, randomization stratification factor (time from stroke onset to randomization4.5 hours (yes/no)), age, sex, baseline NIHSS score, baseline ASPECT score, occlusion location, time from qualifying imaging to randomization. The seed to be used in all MI model is 20201009. The choice of 50 imputations is generally considered sufficient to provide accurate and stable imputed results given the amount of missingness expected in this trial²¹.

Analysis of the primary outcome will then be performed for each of the relevant MI datasets. The results of the 50 analyses will be transformed into a normal statistic and combined into a single analysis using PROC MIANALYZE. Details see Section 6.1.3.

Example SAS code for PROC MI is as follows:

```
PROC MI DATA=ADMRS1 OUT=ADMRS2 SEED=20201009 NIMPUTE=50 NOPRINT;
CLASS TRTP RANDTIME SEX BNIHSS BASPECT OCCLOC BASEMRS MRS2
MRS4 MRS5 MRS6;
FCS LOGISTIC(MRS4 = TRTP AGE RANDTIME SEX BASPECT OCCLOC
BASEMRS / DETAILS);
FCS LOGISTIC(MRS5 = TRTP AGE RANDTIME SEX BASPECT OCCLOC
BASEMRS MRS4 / DETAILS);
FCS LOGISTIC(MRS6 = TRTP AGE RANDTIME SEX BASPECT OCCLOC
BASEMRS MRS4 MRS5 / DETAILS);
VAR TRTP AGE SEX BNIHSS BASPECT OCCLOC RANDTIME IMA_TIME
BASEMRS MRS2 MRS4 MRS5 MRS6;
```

RUN;

In above code, TRTP represents the randomized treatment group, BASEMRS = Baseline mRS score, MRS4 – MRS6 represents the binary mRS responder status at Day 6/discharge (Visit 4), Day 30 (Visit 5), Day 90 (Visit 6) respectively, BNIHSS = Baseline NIHSS score, BASPECT is the baseline ASPECT score (5-7 or 8-10), OCCLOC is the baseline occlusion location, RANDTIME is the time from stroke onset to randomization \leq 4.5 hours (yes/no), IMA_TIME is the time from qualifying imaging to randomization.

The imputation models may be modified based on the actual data if there is an issue in model convergence.

Tipping Point Analysis: Tipping point analysis under missing not at random (MNAR) assumption will be performed as sensitivity analysis to assess the assumptions about the missing primary endpoint data. The tipping point analysis will apply a specified sequence of shift parameters that modify the imputed log odds of mRS response to non-response in the nerinetide group, as follows:

- Missing mRS responder status will be imputed 50 times, following the MI method described above, with adjustment to the log odds of mRS response to non-response by shift parameter S1 in the nerinetide group only. A negative adjustment assumes that a subject with missing response status is more likely to be a non-responder; a positive adjustment assumes the subject with missing response status is more likely to be a responder. The MNAR statement with the ADJUST option in PROC MI will be used to apply the shift parameter.
- 2. Each of the 50 completed datasets applying the shift parameters will be analyzed using the primary analysis method as described in Section 6.1.3.
- 3. The results from the 50 completed datasets will be combined for inference using PROC MIANALYZE.
- 4. Repeat steps 1-3, with adjustment by a different shift parameter to the imputed log odds in the nerinetide group, as following: S1 = 0 (no shift), -0.2, -0.4, -0.6, -0.8, -1.0, -1.2, -1.4, -1.6, -1.8, and -2.0.

The shift parameters that result in a reversed study conclusion (i.e. from statistically significant to non-significant) will be flagged. Alternate series of shift parameters may be applied based on the actual data.

The missing mRS data at one-year follow-up will be handled according to below:

- If subjects are known to be dead before or at one-year follow-up visit, mRS will be assigned a score of 6 and counted as non-responders.
- Other missing data not due to death will be imputed by the multiple imputation method as described above.

4.3.3 Imputation of NIHSS and BI data

No missing NIHSS or BI data due to death. Deceased participants will be assigned scores 42 on the NIHSS and 0 on the Barthel Index (BI) and be counted as non-responders.

Missing NIHSS or BI data at Day 90 will be imputed using the last observation carried forward (LOCF) imputation as follows:

LOCF: Participants who are missing NIHSS or BI endpoint data at Day 90 will have the last

recorded score carried forward, provided that this score was obtained at the Day 30 visit or later. Otherwise, the missing NIHSS or BI will be imputed to the median score obtained at Day 90 in the trial.

For missing BI data at one-year follow-up visit:

- If the subjects are known to be dead before or at one-year follow-up visit, BI will be assigned a score of 0.
- Other missing BI data not due to death will be imputed to the median score obtained at oneyear follow-up in the trial.

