4 TRIAL DESIGN

4.1 Overall Design

This study is a Phase 3, randomized, multicentre, blinded, placebo-controlled, parallel group, single-dose design with a single interim analysis for safety and efficacy. Because AIS is a medical emergency, the trial is designed to enable the administration of standard-of-care treatments without delay in order to save the life of the person concerned, restore good health or alleviate suffering.

Participants harboring an acute ischemic stroke who are selected for endovascular revascularization without intravenous or intra-arterial thrombolytic therapy will be given a single, 2.6 mg/kg (up to a maximum dose of 270 mg) intravenous dose of nerinetide or placebo. Randomization will be stratified by time from stroke onset to randomization ≤ 4.5 hours (yes/no) and done with stochastic minimization to balance baseline factors within strata. The end of the main trial is defined as the date that the last enrolled participant has completed their Day 90 visit/contact. For the purpose of an analytic follow-up sub-trial component, participants will be contacted by telemedicine or telephone at 1-Year by individuals blinded to the outcome of the main trial.

A total of up to 850 male and female participants aged 18 years and older harboring AIS and who are selected for endovascular revascularization without intravenous or intra-arterial thrombolytic therapy will be enrolled.

All participants in the main trial will be followed for 90 days (or until death if prior to 90 days). At Day 30 and Day 90 it is preferred that participants will return to clinic. If an in-clinic visit is not possible the participant can be contacted by telemedicine (preferred) or by telephone (last option).

Participants will be followed at 1-Year for the analytic sub-trial for further outcome assessment by telemedicine or telephone interview conducted by individuals blinded to the outcome of the main trial. This sub-trial will be conducted to explore the independent functioning and quality of life at 1-Year.

Two database locks and corresponding reports are planned for this trial. The first report will be based on the completion of Day 90 visits for the main trial. The second report will be following the completion of the 1-Year follow up for the analytic sub-trial.

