- **Conduct visits by telemedicine or by telephone** at Day 30 and Day 90, where permitted, when a participant is unable to attend the site physically. This will permit the timely collection of efficacy endpoints (mRS, NIHSS, Barthel Index and EQ-5D-5L) and safety data (AE and SAE collection). If the contact is made by phone, only the NIHSS assessment will not be completed, all other assessments will be obtained.
- Use of remote electronic consent, where permitted, to obtain initial consent from the LAR, who may not be able to enter the hospital, and to obtain regained capacity consent from participants who did not consent prior to their discharge from hospital.
- Use of electronic Clinical Outcome Assessments (COA) is optional for the conduct of the mRS, NIHSS, Barthel Index and EQ-5D-5L assessments at Day 30, Day 90 and 1-Year timepoints. If an electronic COA is used, this will permit site staff to collect trial

endpoints even if they are not permitted into the hospital, reduce data entry time and reduce the time on-site for CRAs in order to monitor the data.

In addition to the above items included in the protocol, ongoing risk assessments and monitoring of the COVID-19 situation will be conducted by the sponsor with input from the local investigators at both a site and country level. These ongoing assessments include changes to any of the following:

- Potential impact on trial participants
- Potential impact on trial site staff, including local or central REB/IRBs/ECs
- Potential impact on sponsor/CRO staff conducting site monitoring and central review of data.

The outcome of these ongoing assessments could result in site-specific or country-specific mitigation plans, which could include:

- Suspension of enrollment in that site or country
- Suspension of on-site visits by participants in that site or country, replacing the physical data capture with some remote measures (telephone or telemedicine, where permitted)
- Suspension of on-site visits being conducted by the CRA, replacing the monitoring with remote review of data and telephone contacts with the site
- Other mitigation plans, as appropriate.

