13.2 Assessment Questionnaires

Below is a sample of the assessment questionnaires and instructions to be used in the trial.

Modified Rankin Scale (mRS)	Clinician Reported Outcome
	English example
National Institute of Health Stroke Score	Clinician Reported Outcome
(NIHSS)	English example.
Barthel Index	Clinician Reported Outcome
	English example.
EQ-5D-5L	Patient Reported Outcome
	USA, English Interviewer Administered example
	See https://euroqol.org/ for device, country, and language specific versions

Statistical Analysis Plan

A Multicentre, Randomized, Double-blinded, Placebo-controlled, Parallel Group, Single-dose Design to Determine the Efficacy and Safety of Nerinetide in Subjects with Acute Ischemic Stroke Undergoing Endovascular Thrombectomy Excluding Thrombolysis

(ESCAPE-NEXT Trial)

Protocol NA-1-009

Product:	Nerinetide
IND:	118,087
Sponsor:	NoNO Inc. [name]
Date	18 November 2021
Version	Final 2.0

SIGNATURES OF APPROVAL

Personal Protected Data

Version History

This Statistical Analysis Plan (SAP) for the trial ESCAPE-NEXT is based on Protocol V5.0, dated 18 November 2021.

Version	Date	Change	Rationale
1.0	03 May 2021	Not Applicable	Original version
2.0	18 Nov 2021	- Updated hierarchical testing order of secondary endpoints: moved the NIHSS responder endpoint to the last.	 The change in testing order of NIHSS endpoint was due to the concern of increased missingness of Day 90 NIHSS scores that may impact statistical power. NIHSS cannot be conducted over the phone. Due to COVID-19 there is an increase in the number of Day 90 visits being conducted by phone.
		 Updated the primary analysis model for all binary efficacy endpoints: a generalized linear regression model with adjustment for baseline covariates and randomization stratification factor will be used Changed one of supportive analyses of the primary efficacy endpoint to an unadjusted logistic regression Added robust estimation of unconditional treatment effect for the primary efficacy endpoint analysis 	- The updates in primary analysis model as well as the addition of unconditional treatment effect were made to be aligned with the FDA draft guidance "Adjusting for Covariates in Randomized Clinical Trials for Drugs and Biological Products" dated in May 2021

TABLE OF CONTENTS

SIGNATURES OF APPROVAL		
Version History		
Table of Contents		
List of Tables		
1 Introduction		

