3.4 National Institutes of Health Stroke Scale

The NIHSS is a standardized neurological examination score that is a valid and reliable measure of disability and recovery after acute stroke¹¹. Scores range from 0 to 42, with higher scores indicating increasing severity. The scale includes measures of level of consciousness, extra ocular movements, motor and sensory tests, coordination, language and speech evaluations. The NIHSS will be administered at Baseline, Post-EVT (2 Hours), Day 2, Day 6 (or discharge), Day 30 and Day 90. The NIHSS will only be scored by those trained in the use of this scale. An eCOA tool may be used to conduct this assessment. The NIHSS scores will be dichotomized into 0-2 (indicating a good neurological outcome) versus >2 (indicating otherwise).

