4.3.1 Imputation of Mortality and Worsening of Stroke

For the analysis of rate of mortality, for participants for whom the mortality status is not known at Day 90:

- if they were alive at Day 30, then the subject will be imputed as alive at Day 90
- if both the Day 30 and Day 90 mortality is status is missing, the participant will be imputed as Dead at Day 90.

Worsening of stroke data will be imputed similarly:

- if it's unknown whether the subject experienced worsening of stroke by Day 90 while they did not report any worsening of stroke by Day 30, then the subject will be imputed as not experiencing worsening of stroke at Day 90.
- if both worsening of stroke status is unknown at both Day 30 and 90, then the subject will be imputed as experiencing worsening of stroke at Day 90.

No imputation will be done on the missing one-year follow-up mortality data.

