6.2 Secondary Efficacy Estimand Analyses for Main Study

The primary analysis for the secondary estimands with binary endpoints will be based on the ITT population following the same methods as the primary estimand, and reported as described for each estimand including reporting by randomization strata if the interaction term in the GLM used for the primary pivotal analysis plus the interaction term is significant at the 0.05 level. Missing data will be imputed according to Section 4.3.

Binary secondary endpoints include: mortality rate, NIHSS responder and worsening of stroke.

For the secondary estimand of the "mRS shift analysis", the first step in the analysis will be an adjusted analysis with mRS score 5 and 6 combined, using a proportional odds model to derive the common odds of improvement ("shift") along the mRS scale. The mRS shift analysis will

only be conducted provided that the proportional odds assumption is found to be valid on testing. If it is found to be invalid, the remaining secondary endpoints will be deemed to be protected. Adjustment will include the same variables as the primary outcome analysis.

All tests will be conducted with two-sided level of significance alpha = 0.05 (overall for the in trial), adjusted for the interim analysis per the O'Brien-Fleming boundary spending function. A fixed sequence multiple testing procedure will control the overall experiment-wise error rate for the trial (see below). It pre-specifies that, with all tests conducted at the same pre-specified significance level, the primary endpoint will be tested first, and all subsequent tests are considered failed and deemed exploratory if conducted, in the order specified (primary analysis first, key secondary analysis second, etc.), after the first test which fails. All tests that follow the first failed test, are considered exploratory. The secondary endpoints, and the order they are to be tested, are as they are listed in Table 1: Objectives and Endpoints.

Sensitivity analysis of the secondary estimands will be conducted in ITT population with missing data not imputed.

Additional analysis details of each outcome along with the supportive analyses of the secondary estimands are specified in each section below.

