6.6.4 EQ-5D-5L at 1 Year

The EQ-5D-5L will be obtained by telephone or in-person interview from trial participants at 1 year. EQ-5D-VAS will be analyzed and reported as described in Section 6.3.5.

Table 4: Summary of Inferential Efficacy Analyses

	Endpoint	Primary Analysis*	Sensitivity Analysis*	Supportive Analysis*
Primary	Day-90 mRS Responder (≤2 vs. >2)	Adjusted log-binomial regression model, ITT, SI Estimation of unconditional treatment effect will also be reported.	 Adjusted log-binomial regression model, ITT, OC Adjusted log-binomial regression model, ITT with Day 90 completers only (if missingness ≤ 5%) Adjusted log-binomial regression model, ITT, MI (if missingness > 5%) Adjusted log-binomial regression model, ITT, Tipping Point Analysis (if missingness > 5%) 	 Primary analysis with the interaction term added (treatment by randomization stratification factor) Adjusted log-binomial regression model, ITT, Re-randomization CMH, ITT, SI Unadjusted logistic regression, ITT, SI Adjusted log-binomial regression model, PP, OC
Secondary	Day-90 Mortality	Adjusted log-binomial regression model, ITT Missing data imputed based on Day 30 status	Adjusted log-binomial regression model, ITT, OC	 Mortality Rate: Unadjusted logistic regression, ITT, Missing data imputed based on Day 30 status Adjusted log-binomial regression model, PP, OC Time to Death (Days): Kaplan Meier, ITT, OC Cox proportional hazard regression, ITT, OC
	Worsening of Stroke	Adjusted log-binomial regression model, ITT, Missing data imputed based on Day 30 status	Adjusted log-binomial regression model, ITT, OC	 Unadjusted logistic regression, ITT, Missing data imputed based on Day 30 status Adjusted log-binomial regression model PP, OC
	Day-90 mRS shift (Ordinal)	POM, ITT, SI	POM, ITT, OCPOM, ITT with Day 90 completers only	POM, PP, OC
	Day-90 NIHSS Responder (≤2 vs. >2)	Adjusted log-binomial regression model, ITT, LOCF	Adjusted log-binomial regression model, ITT, OC	 Unadjusted logistics regression, ITT, LOCF Adjusted log-binomial regression model, PP, OC
Tertiary	Stroke volume	Linear regression, ITT, OC	N/A	Student's t-test, ITT, OC
	Day-90 Barthel Responder (<95 vs.≥95)	Adjusted log-binomial regression model, ITT, OC	N/A	N/A
	Day-90 mRS	Adjusted log-binomial	N/A	N/A

	Endpoint	Primary Analysis*	Sensitivity Analysis*	Supportive Analysis*
	Responder (≤3 vs. ≥4)	regression model, ITT, SI		
	Day-90 mRS Responder (≤1 vs. >1)	Adjusted log-binomial regression model, ITT, SI	N/A	N/A

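### The median fallback for missing Day 90 NIHSS gives every affected participant in both arms the same responder status; the effect is modest and the repair is cheap

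*Combined protocol and SAP*

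**What the plan says.** SAP 4.3.3 and protocol 9.3.1 give the same rule in steps. Deaths score 42. If the Day 90 NIHSS is missing, a score from the Day 30 visit or later is carried forward. For anyone left over, "Otherwise, the missing NIHSS or BI will be imputed to the median score obtained at Day 90 in the trial". SAP 3.4 then sets the endpoint: "The NIHSS scores will be dichotomized into 0-2 (indicating a good neurological outcome) versus >2".

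SAP 4.3.3 places the carry-forward and the median fallback under one LOCF label. Tables 4 and 5 name that label for the main NIHSS analysis at the final and the interim: "Adjusted log-binomial regression model, ITT, LOCF". The endpoint is last in the fixed testing sequence, after the primary, mortality, worsening of stroke and, if proportional odds holds, the mRS shift. SAP 6.2 adds: "Sensitivity analysis of the secondary estimands will be conducted in ITT population with missing data not imputed".

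The route into the fallback is stated too. Protocol 13.1 says of Day 30 and Day 90 contacts: "If the contact is made by phone, only the NIHSS assessment will not be completed". The SAP version history explains that NIHSS was moved to the end of the sequence because of a "concern of increased missingness of Day 90 NIHSS scores that may impact statistical power", which it attributes to more Day 90 visits by phone during COVID-19.

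**The concern.** One constant passed through one cut gives one status. A participant phoned at both Day 30 and Day 90 normally has mRS and Barthel on file at both times, yet the rule uses neither. Someone with a Day 90 mRS of 5 could be counted as having NIHSS 0-2, and someone with mRS 0 as not.

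At stake is an alpha-protected test. With equal affected shares and equal deaths, a shared constant shrinks the risk difference while keeping these participants in the denominator. With unequal shares or unequal deaths it adds a difference of its own.

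The SAP also does not say whether the 42s assigned to deaths enter the median. That choice can move the median across 2 and reverse the status of every affected participant.

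**Working it through.** The documents give no NIHSS responder rate, Day 90 median or fallback share, so there is no stated figure to reproduce. What follows is an illustration.

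**Inputs**
- n = 425 per arm (850 randomized 1:1, protocol 9.1). Two-sided 0.05, no interim adjustment.
- Deaths d: protocol 2.1.5 reports a 7.5-point absolute and 39.7% relative reduction in the no-alteplase participants of ESCAPE-NA1. So placebo is 0.075/0.397 = 18.9%, nerinetide 18.9 - 7.5 = 11.4%, and the mean about 15.1%.
- Assumed: p, the true 0-2 rate among all randomized, and f, the fallback share of survivors (5% or 10%, equal by arm).
- c = 1 if the median is 2 or less, otherwise 0. The median is taken over actual scores, so c = 1 when pooled p/(1-d) is at least 0.5.

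**Which side of 2.** For 50% vs 60%, 0.55/0.849 = 64.8% of survivors score 0-2, so c = 1. For 40% vs 50%, 0.45/0.849 = 53.0%, so c = 1. For 30% vs 40%, 0.35/0.849 = 41.2%, so c = 0. In the middle case, if the 42s are included only 45% of all scores are 0-2, the median is above 2, and c becomes 0.

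**Formulas**
- Rule: q = (1-f)p + f(1-d)c, with n = 425.
- Observed cases, deaths kept as non-responders: (1-f)p / k, with n = 425k and k = 1 - f(1-d).
- Power: Wald test of the risk difference, unpooled variance.

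**Worked case** (30% vs 40%, f = 10%, c = 0, deaths 18.9% vs 11.4%)
- Rule: 0.9 x 0.30 = 0.270 and 0.9 x 0.40 = 0.360. Difference 0.090, SE 0.0317, power 81.0%.
- Observed cases: 0.270/0.9189 = 0.2938 (n = 390.5) and 0.360/0.9114 = 0.3950 (n = 387.3). Difference 0.1012, SE 0.0339, power 84.7%.

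**Power (%), rule / observed cases**

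| True rates | Median | Deaths equal, f = 5% | Deaths equal, f = 10% | Deaths 18.9 vs 11.4, f = 5% | Deaths 18.9 vs 11.4, f = 10% |
|---|---|---|---|---|---|
| 50 vs 60 | 2 or less | 80.1 / 81.5 | 76.1 / 79.0 | 83.1 / 83.1 | 82.5 / 82.4 |
| 40 vs 50 | 2 or less | 79.6 / 81.6 | 75.0 / 79.2 | 82.6 / 82.9 | 81.5 / 82.1 |
| 30 vs 40 | above 2 | 84.0 / 84.8 | 81.0 / 82.7 | 84.0 / 85.8 | 81.0 / 84.7 |

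On the log relative-risk scale with equal deaths and f = 10%, the pairs are 75.3/78.1, 74.2/78.3 and 80.0/81.6, so the costs are almost the same.

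Observed cases is the plan's own comparator, not an unbiased one. When deaths differ it slightly overstates the difference (10.1 points in the worked case against a true 10.0), because only survivors drop out.

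**No true NIHSS difference, f = 10% in both arms, deaths 18.9% vs 11.4%**
- c = 1: the rule adds 0.10 x (0.886 - 0.811) = 0.75 points; rejection is 5.6%.
- c = 0: nothing is added.

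**Unequal fallback, no true effect, equal deaths**
- 10% vs 12%: 0.6-0.8 points and 5-6% rejection.
- 10% vs 15%: 1.5-2.0 points and 7-9% rejection. The sign depends on the side of 2.

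**The case against.** The strongest reply is that little is at risk. Telephone is the last option for follow-up, a Day 30 score rescues many Day 90 phone visits, the endpoint is tested last, and observed-case analyses are planned. NIHSS also stays alpha-protected only after a mortality benefit has been shown, so the equal-deaths column fits the test poorly. All of this stands, and it is why the unequal-deaths figures carry more weight here. They do not remove the cost when the median is above 2.

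Two stronger readings are tempting and should not be drawn.

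- **Many wrong statuses.** A reader might infer harm because 35-47% of fallback participants would be misclassified if they resemble other survivors. That is not evidence against the rule. With r the share of survivors scoring 0-2, random draws without predictors are wrong 2r(1-r) of the time: 45.6%, 49.8% and 48.5% in the three scenarios, against 35.2%, 47.0% and 41.2% for the constant. The case for multiple imputation rests on using informative predictors, and that gain cannot be quantified from the documents.
- **Inflated type I error.** A reader might infer 7-9% rejection. That needs something like 10% vs 15% fallback. The trial is blinded and the SAP attributes phone visits to COVID-19, so nothing in the documents points to such an imbalance. With about 361 survivors per arm (425 x 0.849), a gap of 5 points around 12.5% has SE sqrt(2 x 0.125 x 0.875/361) = 2.5 points, so chance produces one that large about 4% of the time.

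It is also fair to say that the Day 30 carry-forward ignores recorded Day 90 mRS and Barthel. It does at least use the participant's own NIHSS, so it can reasonably stay.

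**Conclusion.** The point holds as a minor, inexpensive improvement. The rule assigns one shared status to everyone in the fallback, discards recorded information on those participants, and leaves open whether deaths enter the median that decides the status.

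Under the assumed rates, the power cost against observed cases is about 1-2 points at 5% fallback and 2-4 at 10% with equal deaths. In the more relevant setting, with deaths as in ESCAPE-NA1, it is about 0-0.6 points if the median is 2 or less and 1.8 to 3.7 points if it is above 2. In that setting, with a median of 2 or less and 10% fallback, the death difference alone produces 0.75 points and 5.6% rejection when NIHSS does not truly differ. Every figure depends on a fallback share and responder rates that the documents do not give. The primary endpoint is not affected.

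Three related texts also need reconciling, though none would merit a point alone:
- **Unknown vital status.** SAP 4.3.1 says "if they were alive at Day 30, then the subject will be imputed as alive at Day 90". Section 4.3.2 gives that same participant mRS 6 if Day 90 status is unknown and there is no Day 30 or Day 90 mRS. Section 4.3.3 does not say which status governs NIHSS.
- **Carry-forward window.** SAP 4.3.3 counts a score from the Day 30 visit itself; 6.2.4 refers to ratings after Day 30.
- **Barthel.** SAP 4.3.3 imputes the Day 90 score; Table 4 analyses it on observed cases.

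**What to change.** Amend SAP 4.3.3 and protocol 9.3.1, with matching entries in Tables 4 and 5:

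1. Drop the median fallback for Day 90 NIHSS and keep the carry-forward.
2. Multiply impute the remaining missing responder status among participants not counted as dead, adapting the FCS logistic procedure of SAP 4.3.2. Predictors: treatment, the stratification factor, all baseline covariates listed there, Day 2 and Day 6 NIHSS, and Day 30 and Day 90 mRS and Barthel. Include baseline NIHSS and imaging-to-randomization time explicitly, because the example FCS statements omit both although the text lists them. Combine with PROC MIANALYZE as in SAP 6.1.3.
3. Keep observed cases as the sensitivity analysis.
4. State which vital-status rule governs NIHSS, use one carry-forward wording in 4.3.3 and 6.2.4, and reconcile 4.3.3 with Table 4 for Barthel.

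The question of whether the 42s enter the median then no longer arises for Day 90 NIHSS.

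The cost is wording and one more imputation model; the predictors are already scheduled for collection. The downside is that the method would differ from the single imputation used for the primary mRS analysis.
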